We will evaluate the impact of DHP's quality improvement pilot program (called, *Nurture*), which included nutrition education and food support offered to a subset of pregnant women aged 30 years and above and were covered by the Medicaid Managed

Care Organization (MCO) plan in their “STAR” and “CHIP” programs during October 2022 and July 2023.

From this population, DHP randomly selected a subset of approximately 500 women during that period, from which approximately 200 were in the program, the “exposed group.” The women who were covered during the same period but were not selected were not exposed to the program and will compose the “comparison group.”

The objective is to compare maternal and neonatal outcomes between those who participated in the program (exposed group) and those who did not (comparison group).

Analysis Plan:

Claims data will be pulled retrospectively from the insurer's database and other administrative sources. Information will include healthcare utilization, maternal outcomes during pregnancy, and neonatal outcomes at and post-delivery. The primary analysis involves comparing the outcomes of the exposed group with the comparison group. Statistical methods appropriate for this type of administrative data will be employed to assess the differences between the two groups, adjusting for potential confounders.

The *Nurture* program’s impact will be evaluated using claims data received from DHP concerning two composite outcomes: adverse maternal health outcomes (Composite 1) and adverse neonatal outcomes (Composite 2), as shown in Table 1 below. In addition, we will explore single outcomes, such as delivery mode (vaginal vs c-section), cost data, and birthweight, adding nuance to our understanding of the program's impact.

We will primarily use logistic regressions to predict the primary, binary composite outcomes for mothers and newborns, adjusted for risk factors such as maternal age, gestational age at the time of enrollment, pre-existing diabetes, hypertension, and being overweight pre-pregnancy (shown in Table 2). The program “dose” variables are anticipated to be continuous predictors that include both ‘usual care’ (i.e., prenatal care visits) and *Nurture* program elements (the dollar value of the gift cards spent up to 30 days after stopping the program, total number of nutrition consult minutes); see Table 3.

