Because we expect cost data to be continuously distributed, linear regressions are expected to be more appropriate. The predictors will remain the same in all models irrespective of outcome, including the “dose” variables.

Table 1. Program outcomes from health claims

Composite outcome 1: Adverse health events during pregnancy	Composite outcome 2: Adverse health events at birth and newborn-related	Exploratory outcomes:

 • Gestational Diabetes Mellitus • Excessive weight gain during pregnancy • Pregnancy-associated hypertension 	
 • Pre-term birth (<37 weeks) • Neonatal Intensive Care Unit (NICU) • Small for gestational age • Large for gestational age • Stillbirths 	
 • Emergency Department visits • Cost (outpatient, inpatient, pharmacy, total) • Delivery mode (vaginal, c-section) • Birthweight collected from hospitals

Table 2. Population descriptors and demographics from health claims

Demographics	Health history (dichotomous)

 • Age (years) • Ethnicity • Location (Nueces/Hidalgo) • Gestational age at enrollment • Gestational age at delivery 	
 • Family history of diabetes mellitus • Pre-pregnancy diabetes mellitus • Pre-pregnancy overweight/obesity • History of gestational diabetes • Chronic hypertension

Table 3. “Dose” variables from program implementation tracking and health claims

Nurture Program uptake	Care Received

 Gift card usage (dollar amount) Packages received (counts) Nutritional consults (duration) 	
 Prenatal visits (counts) Referral to Case Management (dichotomous)

DHP’s Nurture enrollment:

1. DHP receives daily new health plan enrollees from the TX State. Their data analytics team identified new pregnant members aged 30 or older in bi-weekly “cycles” and ran an algorithm to randomly select a list of names to be notified and contacted by DHP’s Community Health Workers (CHWs).
2. Notifications: Members on the roster to be called received an SMS text with a URL to an informational page, which was also mailed as a hard copy to the member’s address on file.
3. Welcome calls: DHP’s CHWs called up to 3 times on consecutive days to welcome the women to the *Nurture* program, explain what to expect, confirm address for mailing out the packages, and book two phone nutritional consultations.

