Members of the Driscoll Health Plan could be enrolled in the program if they were pregnant and aged 30 years or older at the time of DHP enrollment.

15 **Total Sample Size**

To input text click in the light grey area below.

We expect to receive data from approximately 1700 DHP members broken down as the following (approximate numbers):

- Exposed group: DHP selected 511 members between October 2022 and July 2023, of whom 224 were contacted and opted into the Nurture program.
 - CHWs could not reach the remaining 287 women on the list and, therefore, could not confirm address and book consultations. We will receive the demographic data on this group to explore how they compare with the other two groups in terms of their population descriptors (Table 2 in section 3).
- Comparison group: approximately 1200 women who were 30 years old or older and pregnant during the same enrollment period and were not selected during the DHP's enrollment process.

16 Sample Size Rationale

Provide justification for the sample size and its adequacy for answering the research question.

To input text click in the light grey area below.

Data coming from claims are mostly binary, which is characterized by limited variability and increased uncertainty in proportions. This fact makes detecting statistically significant differences more challenging, requiring larger sample sizes to ensure the reliability of the findings in such studies using these binary outcomes—which is the case of Nurture.

Statistical power is critically dependent on the base rate of the outcome metrics among the comparison subjects. But, when the comparison group is composed of unmatched subjects that is at least four times the size of the exposure group, statistical power tends to be maximized.

That being said, the analysis needs to include all women as described in the previous section.

Because we do not know the incidence rate of the outcomes of interest, we estimated the effect sizes we can capture at 80% power with $\alpha = 0.05$ assuming different rates among comparison subjects (30% and 35%) and four different rates among exposed subjects (25%, 23%, 20%, 18%).

Table 4 demonstrates the statistical power to detect differences between the exposed and comparison groups, assuming *Nurture* produces certain effects. If the composite outcome rate is around 30% among comparison subjects, we have enough power to

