detect rates of 20% or lower among exposed subjects (yellow highlight). If the rate is closer to 35% among comparison subjects, we have enough power to detect rates of 25% or lower among exposed subjects (blue highlight).

Table 4. Statistical power at alpha = 0.05 to detect the program effects of interest assuming two different base rates among comparison subjects.

		% rate among exposed			
		25%	23%	20%	18%
% rate among comparison subjects	35%	78	90	98	99
	30%	28	46	80	93

17 Confidentiality and Data Security Plan

Describe how you will protect confidentiality of the subjects and the security of the data or specimens. Describe where you will store the data or specimens, who will have access to data or specimens; and the data and specimen retention and destruction timelines.

To input text click in the light grey area below.

DHP's data analysis team will anonymize and remove all PHI from all data sets prior to sharing in a way so that no information can be linked back to the individuals.

Data for analysis will be saved as Excel files and, subsequently, in formats specific for analyses using specialized statistical software, in a UT Box folder accessible only to team members involved in the data analysis, such as the PI and the biostatistician.

Data sets will be destroyed (permanently deleted) 3 years after all analyses are completed.

WAIVER OF INFORMED CONSENT

Complete this section if you are seeking a waiver of informed consent for the collection of identifiable data or biospecimens.

To approve a waiver or alteration of informed consent all of the following criteria below must be justified by the researcher.

Only complete the sections below if requesting a waiver of informed consent for the use of readily identifiable data or specimens and the data use is not regulated by HIPAA.

If research solely involves HIPAA protected data, skip this section and complete the Waiver of HIPAA Authorization section below.

18 The research involves no more than minimal risk to the subjects.

To input text click in the light grey area below. Provide protocol specific rationale as to how this study meets this requirement.

19 The waiver or alteration will not adversely affect the rights and welfare of the subjects.

To input text click in the light grey area below. Provide protocol specific rationale as to how this study meets this requirement.

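### Do the exploratory cost regressions need a prespecified robust standard error?

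*Combined protocol and SAP*

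**What the plan says.** Under Analysis Plan in section 3, the two binary composites are to be analysed by logistic regression. For cost the plan says "Because we expect cost data to be continuously distributed, linear regressions are expected to be more appropriate". It adds that "The predictors will remain the same in all models irrespective of outcome", so the cost models carry the same risk factors and dose variables as the logistic models.

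Table 1 lists four cost measures among the exploratory outcomes, and the text above it says "we will explore single outcomes, such as delivery mode (vaginal vs c-section), cost data, and birthweight". The section also makes a general commitment to methods suited to administrative data. It names no variance estimator, transformation, bootstrap or residual check for cost.

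Section 15 gives the group sizes: "DHP selected 511 members between October 2022 and July 2023, of whom 224 were contacted and opted into the Nurture program", and a comparison group of "approximately 1200 women who were 30 years old or older and pregnant during the same enrollment period".

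**The concern.** The one reason given for linear regression is that cost is continuous. That supports modelling a mean, but the classical standard error also needs the same residual variance in both groups. With equal group sizes, unequal variances would largely cancel in an unadjusted comparison. With a split of about 1 to 5.4 they do not, and a larger sample at the same ratio would not help.

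If the exposed women had the larger cost variance, classical intervals would be too narrow, and a chance difference could be read as a saving or an added cost. If they had the smaller variance, intervals would be too wide and a real difference could be missed. Cost claims about a health-plan programme are easily quoted, even when labelled exploratory.

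**Working it through.** **Inputs.** Group sizes of 224 and 1200 come from section 15. The significance level of 0.05 is stated in section 16 for the power calculation; two-sided testing is assumed here. The documents give no cost mean, SD or effect size, so there is no cost figure to reproduce, and the exposed-to-comparison SD ratio *r* is an assumption throughout.

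**Step 1: classical standard error, unadjusted contrast.** Set the comparison SD to 1.

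- Pooled variance = (223*r*² + 1199)/1422
- Classical SE = √[pooled variance × (1/224 + 1/1200)]
- True SE = √(*r*²/224 + 1/1200)
- Actual two-sided error = 2[1 − Φ(1.96 × classical SE / true SE)]

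For *r* = 1.25 the pooled variance is (348.4 + 1199)/1422 = 1.088. The classical SE is √(1.088 × 0.005298) = 0.0759 and the true SE is √(0.006975 + 0.000833) = 0.0884. Their ratio is 0.859 and the error is 9.2%.

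| Assumed *r* | Classical SE / true SE | Two-sided error |
|---|---|---|
| 0.5 | 1.55 | 0.2% |
| 0.8 | 1.16 | 2.3% |
| 1 | 1.00 | 5.0% |
| 1.25 | 0.86 | 9.2% |
| 1.5 | 0.76 | 13.5% |
| 2 | 0.65 | 20.6% |

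**Step 2: can *r* be read from the plan?** Section 16 considers a comparison rate of 30% and says the study can "detect rates of 20% or lower among exposed subjects". If cost had two levels that followed these rates, *r* would be √(0.20 × 0.80 / (0.30 × 0.70)) = 0.873, and the Step 1 formula would return about 3.1%. That figure is not a type I error. With rates of 30% and 20% the mean costs differ, so the null hypothesis is false. With equal rates the variances are equal too, and simulation at 30% v 30% gives 5.1%. What changes at 30% v 20% is power: 88.1% with the classical SE and 90.0% with a robust SE, a gap of 1.9 points. The rates also describe the binary composites, not cost. The documents therefore supply no value of *r* for cost.

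**Step 3: is a robust SE better?** Two-group simulations used lognormal costs with equal means, 224 v 1200. CV is the coefficient of variation, exposed v comparison.

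| CV | Classical error | HC3 error |
|---|---|---|
| 1 v 1 | 4.9% | 5.5% |
| 2 v 1 | 19.5% | 8.6% |
| 2 v 2 | 4.9% | 6.8% |
| 2.5 v 2 | 7.9% | 8.8% |
| 3.75 v 3 | 7.2% | 9.7% |

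Large repeat runs moved single figures by up to about half a point. HC3 wins clearly when the SD ratio is large. It loses when costs are strongly skewed and the ratio is 1 or 1.25, because it relies on the variance estimated from 224 skewed values, whereas the pooled variance is steadied by the 1200. A bootstrap does not resolve this: at CV 2 v 2, in a smaller simulation of 2000 runs, the percentile and bootstrap-t intervals both had 8.8% error against 4.7% for the classical SE.

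**Step 4: the planned dose terms.** Gift-card dollars and consult minutes are zero in the comparison group. In a simulated dose model with comparison CV 1, classical error for the gift-card term was 5.1%, 9.2% and 19.8% at *r* = 1, 1.25 and 2; HC3 gave 5.9%, 6.3% and 7.7%. With CV 2 in both groups, classical error was 5.5% (gift cards) and 5.9% (minutes), and HC3 gave 7.3% and 5.4%. The pattern is broadly that of the two-group case. The covariate distributions are assumed, and the model leaves out packages received and case-management referral, both of which are in Table 3.

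**The case for a change.** The strongest case for a change is that an unstated standard error usually means the software default, which is classical. Equal variance is also not a safe assumption here. The exposed women are those "of whom 224 were contacted and opted into the Nurture program", a reached and willing subset of the women selected, so their residual variance could differ even if the programme did nothing. Naming an SE type costs a sentence or two, and doing so before results are seen removes a choice that could otherwise be made after the fact.

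Much of this stands. Continuity is an incomplete reason, the arithmetic in Step 1 is right, and stating the SE type would be a harmless clarification. What does not stand is the step from there to a prescribed method. The size and direction of any error are unknown, and the favourable HC3 results come from low skew or a large SD ratio. With strongly skewed costs and a modest ratio, prescribing HC3 or a bootstrap interval would raise false positives.

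**Conclusion.** No change to the plan follows. The plan leaves the SE type for the cost models open; it does not commit to a wrong one. Its wording on cost is tentative, and a robust SE, or a gamma log-link model as a sensitivity analysis, would be consistent with it. Unequal variances do not bias the estimated mean differences. Cost is exploratory, and neither the sample size nor a primary conclusion depends on it.

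If classical SEs were used, the two-sided error would be 5% at equal variances, 9.2% at an SD ratio of 1.25 and 20.6% at 2, but each ratio is an assumption that the documents neither support nor exclude. The main alternative improves on this in some plausible settings and worsens it in others: 19.5% falls to 8.6% at CV 2 v 1, while 4.9% rises to 6.8% at CV 2 v 2. Analysts can make that trade-off sensibly once the spread and skewness of costs are known, provided the report states which SE was used.

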In response, DHP, with input from our Factor Health lab at Dell Medical School, introduced the Nurture program for its members as a quality improvement initiative, designed to expand members' access to nutrition education and food purchase support to improve health and pregnancy outcomes.

DHP's Nurture Program:

The *Nurture* program focused on promoting healthy eating through nutrition education and food purchasing support with monthly gift cards for a main local grocery store at the Corpus Christi area. Specifically, the program includes the following components:

- 1. Nurture Monthly Packages:** Sent every four weeks until the member reaches the end of pregnancy (delivery or other reasons, e.g., miscarriage), with a maximum of eight packages. Each package includes:
 - A US\$40 gift card (2 x \$20 each) to a grocery store.
 - A healthy eating information sheet selected from Brighter Bites project (<https://brighterbites.org/>).
 - A set of three recipes.
 - Nutrition-related Frequently Asked Questions (included in four out of the eight packages).
- 2. Two 30-Minute Nutritional Consultations over the phone:** Designed by a Registered Dietitian Nutritionist (RDN) who trained a bilingual nutrition specialist to deliver the consultations. Topics revolved around healthy eating during pregnancy, such as food choices, portion sizes, budget-friendly shopping, food safety, and food preparation. No nutrition therapy advice to manage diseases was provided.

Members had the flexibility to opt out of the program at any time and discontinue receiving packages. Consultations were optional. If they opted out, they continued to receive the DHP benefits as part of their regular coverage.

Secondary Data Analysis Proposal: With funding from the Episcopal Health Foundation, we will conduct a secondary data analysis to evaluate the DHP's Nurture program using their existing administrative data from claims.

Kolkhorst (2019). *Relating to maternal and newborn health care and the quality of services provided to women in this state under certain health care programs.* (S.B. 750). 86th Legislature, Regular Session.
<https://capitol.texas.gov/BillLookup/History.aspx?LegSess=86R&Bill=SB750>.

3 Design, Methodology, and Data Analysis

Provide information regarding study design or data collection methodologies. Describe the data analysis plan, including any statistical procedures or power analysis.

To input text, click in the light grey area below.

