 - Individuals who could not be reached by the CHW did not receive the packages and the consultations but continued to receive their regular benefits as part of their DHP membership.

The end of participation in the program is marked by the termination of pregnancy (in the form of a claim to the health plan that would flag delivery or a miscarriage/abortion/stillbirth). If such a claim does not reach DHP's system in a timely manner, the woman in the *Nurture* program could receive up to 8 mailout packages.

The Texas Health and Human Services Commission (HHSC) reviewed and approved key member-facing materials, such as SMS text and the informational letter, as part of their regular review process of member-facing materials.

Third group: The women who were selected to be offered the program, but DHP staff could not connect during telephonic outreach, compose a third group. Administrative data on this group will enable us to explore how they compare with the other two groups in terms of their population descriptors and demographics shown in Table 2 above. Answering evaluation questions such as how do those who were reached by the CHWs differ from those who weren't, helping to assess reach from an equity perspective.

4 Data or Specimen Information

Provide information about where the data or specimens will come from (e.g., pathology lab, commercial sources) and what type of data or specimens you will obtain.

To input text click in the light grey area below.

DHP data analysis team will leverage internal databases to compile the required administrative data for analyses, which will be shared as Excel spreadsheets via secured File Transfer Protocol (sFTP).

DHP also contracted the Dell Med lab (Factor Health) services for the delivery of the nutritional consultations and to track gift card balances. These data are owned by Driscoll, who will receive the full data set, de-identify and anonymize it, and merge it to the other relevant sets they will generate for analysis.

The staff involved in the delivery of the nutrition consultation service will not be involved in the data analysis in any way.

5 Identifiers

List all identifiers the researcher will obtain even if the researcher plans to make the data or specimens anonymous. Include information that can be linked directly or indirectly to the subject.

To input text click in the light grey area below. List all identifiers collected.

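### Gift-card dollars and prenatal visits accrue until delivery yet are predictors in the Composite 2 model, and with dose terms in every model none estimates the planned group contrast

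*Combined protocol and SAP*

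**What the plan says.** The Analysis Plan in Section 3 states the aim as a group contrast: "The primary analysis involves comparing the outcomes of the exposed group with the comparison group". Section 16 powers the same contrast: "Table 4 demonstrates the statistical power to detect differences between the exposed and comparison groups".

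The predictors named for the logistic models are baseline risk factors and continuous dose variables. The dose variables are prenatal visits and two program measures, "the dollar value of the gift cards spent up to 30 days after stopping the program, total number of nutrition consult minutes". Table 3 also lists packages received and case-management referral. No group indicator is named, and none is excluded. The text before Table 1 then fixes one predictor set, dose included, for every outcome: "The predictors will remain the same in all models irrespective of outcome".

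On accrual, Section 2 says of the packages: "Sent every four weeks until the member reaches the end of pregnancy", with a cap of eight. The enrollment text in Section 3 ends participation at a claim for delivery or loss, and adds that if the claim is late a woman "could receive up to 8 mailout packages".

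Table 1 puts preterm birth and stillbirth in Composite 2. Table 2 lists "Gestational age at delivery" among the descriptors. It is not one of the adjusters named in the text, but that list is given as examples with a pointer to Table 2, so its status is open.

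**The concern.** There are two linked problems.

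**The outcome partly sets the predictor.** Dollars, packages and visit counts accumulate over a period that delivery closes. A preterm birth is a Composite 2 event and also the reason the count is low. Adjusting for gestational age at enrollment accounts for when accrual starts, not when it stops. Birthweight, an exploratory outcome, has the same problem because it too depends on pregnancy length.

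**The planned contrast is not estimated.** Program doses are zero for every comparison woman. If a group term is kept beside dose, its coefficient is the contrast at zero dose, which is not the planned effect. If dose replaces group, the model has no exposed-versus-comparison coefficient, and Table 4 does not describe its power.

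At stake is a report in which a useless program seems to show that spending protects newborns while participation harms them, or in which a real effect of the planned size is missed because the coefficient read is not the one that was powered.

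**Working it through.** **1. Table 4.** With 224 exposed and 1200 comparison women (Section 15), the two-sided pooled z-test power is Φ[(|p_c − p_e| − 1.96·SE₀)/SE₁], where SE₀ uses the pooled rate and SE₁ the separate rates. For 30% versus 20%:

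- pooled rate = (1200×0.30 + 224×0.20)/1424 = 0.2843
- SE₀ = 0.03283; SE₁ = 0.02982
- power = Φ[(0.10 − 0.06435)/0.02982] = Φ(1.196) = 88.4%

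| Comparison rate | Exposed 25% | 23% | 20% | 18% |
|---|---|---|---|---|
| 35%, stated | 78 | 90 | 98 | 99 |
| 35%, recomputed | 84.6 | 95.4 | 99.7 | 100.0 |
| 30%, stated | 28 | 46 | 80 | 93 |
| 30%, recomputed | 32.0 | 56.8 | 88.4 | 97.3 |

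The stated figures are not reproduced at these sizes. About 176 versus 1200 would match them within 2 points; the plan does not give the n it used. That is a separate matter. What counts here is that Table 4 concerns two proportions with no dose terms.

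**2. Accrual on the plan's own schedule.** Assuming the first package goes out at enrollment, packages = min(8, floor((weeks at delivery − weeks at enrollment)/4) + 1), at 40 dollars each.

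| Enrolled at | Delivery at 28 wk | 32 wk | 36 wk | 40 wk |
|---|---|---|---|---|
| 16 wk: packages (dollars) | 4 (160) | 5 (200) | 6 (240) | 7 (280) |
| 24 wk: packages (dollars) | 2 (80) | 3 (120) | 4 (160) | 5 (200) |

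The eighth package falls 28 weeks after the first, so the cap stops accrual before 37 weeks only if enrollment is before 37 − 28 = 9 weeks.

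**3. Simulation.** From the plan: 224 versus 1200, 5% level, comparison rate 30%, package interval, cap and card value. Assumed, because the plan gives no figures:

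- preterm rate 8–15%; enrollment at 8–24 or 6–30 weeks; claim lag 0 or 4 weeks
- term delivery Normal(39.1, 1) limited to 37–42 weeks; preterm delivery at 37 weeks minus an exponential with mean 2.8 weeks
- Composite 2 = preterm birth or an independent component, 30% in total
- first package 2 weeks after enrollment; dollars = 40 × packages × Beta(6,2)
- consult minutes 0, 30 or 60
- visits = 80% of those scheduled, or Beta(4,2) attendance that varies between women

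Models adjust for gestational age at enrollment and age, with 800–1000 trials per setting.

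*No program effect, Composite 2, rejection rates:*

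| Model | Dollars | Group |
|---|---|---|
| Group + baseline covariates | – | 4–6% |
| Group + dollars | 17–73% | 16–69% (false-harm OR 1.5–3.7) |
| Group + dollars + minutes + visits | 6–22% | 6–20% |
| Same, attendance varying between women | up to 42% | up to 36% |
| Dose replacing group | 5–13% | no such term |

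- The visits coefficient is falsely protective in at least 99.7% of trials in every setting, with group kept or replaced.
- In the group + dollars base case, the 52% for dollars falls to 46% and 35% with 4- and 8-week claim lags, and to 33% and 24% with 15% and 30% opt-out.
- Composite 1: dose and group terms reject in 3–8%, so this mechanism does not inflate its error rate.
- Birthweight (assumed 130–190 g per week), group + dollars: dollars reject in 46–90%.

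*True effect, 30% versus 20%, same benefit for every participant:*

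| Model and test | Composite 2 | Composite 1 |
|---|---|---|
| Group only | 85–90% | 85–90% |
| Group term, with dollars, minutes and visits | 1–4% | 11–17% |
| Dollars, dose replacing group | 50–58% | 36–44% |

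When dose replaces group, a joint test of dollars and minutes detects the effect in 72–84%.

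**4. Check of the remedy.** Dose accrued by a 28-week landmark, entered beside group, rejects in 4–6% under no effect.

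**The case against.** The strongest reply accepts the mechanism and disputes its weight.

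- **The plan does not say group is dropped.** Section 3 names the group comparison as primary, and a separate group model is not ruled out. This is right: the defect is an unspecified model, not a documented replacement. But the same-predictors rule covers all models, so as written no described model gives the contrast.
- **The largest error rates come from group + dollars,** which leaves out minutes and visits. Also right. For the full named set the inflation is smaller, and in null trials of that model a significantly protective dollars term together with a significantly harmful group term appeared in 5–13% (12–20% with uneven attendance). Most null trials would not show both.
- **Visits are labelled usual care.** A false visits coefficient alone does not mislead about the program: with group and visits only, the group term rejected in 5–7% under no effect and kept 92% power for Composite 2. The coefficient would still be reported as protective almost regardless of the truth.
- **Low power of the group term is expected when it is a zero-dose contrast.** A joint 3-df test of group, dollars and minutes detected the effect in 79% (Composite 2) and 70% (Composite 1), with null rejection of 7–9% (12–19% with uneven attendance). So the signal is spread over several terms rather than lost. The plan specifies no such test, and it loses power and exceeds the nominal level.
- **Several inputs are undocumented,** and an effect unrelated to dose is the case least kind to dose terms. This limits the sizes, not the direction.

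**Conclusion.** The concern holds and must be fixed before any model is fitted. The direction follows from the plan's own package schedule and its definition of Composite 2.

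The sizes rest on assumed preterm rates, enrollment timing, card use and visit attendance, and they differ by model. They are modest for dollars when dose replaces group, moderate for the full named set beside group, and large for dollars alone beside group. Late claims, the eight-package cap and opt-out weaken the link without removing it. Error rates for Composite 1 are unaffected, but its group term also loses most of its power once dose is added. The birthweight result is exploratory and does not carry the conclusion.

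**What to change.** Replace the rule in Section 3 that one predictor set, dose included, enters every model. Suggested text:

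*Each primary model contains a group term (exposed versus comparison) plus covariates fixed before selection. Gift-card dollars, packages, consult minutes, prenatal visits and case-management referral are not in these models. Gestational age at delivery is a descriptor, not a covariate.*

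Report dose as exploratory only: dose accrued by a fixed gestational landmark (28 weeks, for example), among women enrolled before it and still pregnant at it. If dated package and card records are not available, report dose descriptively.

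**Cost.** The primary models need wording only; they use data already planned and keep the stated contrast, which is the one Table 4 addresses. The landmark analysis needs dated records. Section 4 says the lab was contracted "to track gift card balances", and the 30-day spending cut-off implies some dating, but this must be confirmed. Because no identifiers are shared, the health plan would have to supply a derived total for each woman.

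The price is that dose-response becomes exploratory and loses women who deliver before the landmark or enroll after it. The latter are about (30 − 28)/(30 − 6) = 8% if enrollment is uniform over 6–30 weeks. Whether to compare all selected with non-selected women is a separate question that this change leaves open.
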